5.3.2.5 Management of CNS Adverse Events

If a patient reports any clinical AE of any grade during the administration period of APR-246 that could be considered to originate from the CNS (e.g., dizziness, tremor, vertigo, nausea), then the patient will be given a rescue medication as per the institutional standard of care.

Dose modifications have been successfully used to manage potential CNS effects occurring during the infusion (Table 11). For any clinical AE grade ≥ 3 , the infusion should be interrupted and if the AE resolves to CTCAE grade ≤ 1 within 2 hours, the infusion may be resumed at the same infusion rate. If

the same symptoms recur or increase in severity during re-challenge, the infusion should be interrupted.

If the event lasts longer than 2 hours, then the APR-246 infusion should be discontinued for that day and the remaining drug should be discarded.

Table 11. Management of CNS Adverse Events (e.g., Dizziness, Tremor, Confusion, and Ataxia)

Worst toxicity	Dose Modifications for APR-246
Grade 1	Maintain dose level
Grade 2	If resolved to grade ≤ 1 with medical therapy, continue same dose level If not resolved despite treatment interruption and maximal medical therapy, stop infusion and \downarrow 1 dose level for subsequent dose. If unable to reduce APR-246, discuss with study Medical Monitor before resuming or discontinuing APR-246.
Grade ≥ 3	Stop infusion and give medical therapy. If resolved (to grade ≤ 1) with medical therapy in ≤ 2 hours from onset, infusion may resume at the Investigator's discretion. If not resolved despite treatment interruption and maximal medical therapy, infusion should be discontinued for that day. \downarrow 1 dose level for subsequent dose. If unable to reduce APR-246 dose, discuss with study Medical Monitor before resuming or discontinuing APR-246.
Grade 4	Permanently discontinue patient from APR-246.

In prior APR-246 studies, prochlorperazine 10 mg PO three times daily, anti-emetics (e.g., ondansetron), or medication(s) to treat motion sickness (e.g., meclizine) have been used for prophylaxis and/or to treat CNS-related AEs that have occurred during treatment with APR-246. Prochlorperazine, anti-emetic, or motion sickness medication(s) should be administered as clinically indicated to prevent or treat CNS-related AEs while subjects are receiving treatment with APR-246. When prophylaxis is clinically indicated, it is recommended to start prochlorperazine, anti-emetic, or motion sickness medication(s) at least one day prior to the scheduled dose of APR-246. Please follow dose administration guidelines in the current USPI for prochlorperazine, anti-emetic, or motion sickness medication(s). The US label for prochlorperazine does not list QT interval prolongation as a known risk associated with use of this drug.

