4.0 TRIAL DESIGN

4.1 Overview of Trial Design

Treatment will be administered on an outpatient basis but may be administered in the inpatient setting for patients who are hospitalized and meet criteria for study enrollment. No investigational or commercial agents or therapies other than those described below may be administered with the intent to treat the patient's disease under study.

Monotherapy Cycle

There is a 7-day monotherapy cycle where patients receive APR-246 IV on Day 1 and APR-246 PO on Day 2. The primary purpose of the monotherapy cycle is to obtain peripheral blood for monotherapy PK and PD analyses following IV and PO administration of APR-246.

Patients will start treatment with APR-246 IV as a single agent administered on Day 1 of a single 7-day monotherapy cycle at the assigned cohort dose level, prior to Cycle 1 Day 1 of combination therapy. On Day 2 of the 7-day monotherapy lead-in period, patients will receive a single dose of APR-246 administered PO at the dose of 500 mg. After review of oral PK data from at least 6 patients, a decision can be made whether to increase the PO dose of APR-246 and/or administer APR-246 with a standard high-fat meal to investigate, respectively, dose linearity in PK and/or the effect of food on oral absorption of APR-246. Dose escalation of the oral dose or switching to administration with food will be determined by PK to ensure that the APR-246 exposure levels after oral dosing do not exceed the exposure levels after IV administration in terms of C_{max} and AUC.

Combination Treatment

After the APR-246 monotherapy lead-in, study treatment will consist of APR-246 administered as an IV infusion at the same assigned dose that was used during the monotherapy lead-in period once weekly, on Days 1, 8 and 15 of each cycle, concurrently with venetoclax for the 5-week ramp-up at the dose of 20 mg during Week 1, 50 mg during Week 2, 100 mg during Week 3, 200 mg during Week 4, and 400 mg during Week 5. Beginning Cycle 2 Day 1, venetoclax will be administered at 400 mg (or tolerable dose following 5-week ramp up) PO daily. IV rituximab will be initiated at 375 mg/m² on Cycle 2, Day 2 and then administered at 500 mg/m² on Day 2 of Cycles 3-7. After 6 cycles of treatment with APR-246 in combination with venetoclax + rituximab, APR-246 + venetoclax will continue to be

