Upon determination of the pharmacologically active dose or MTD, or when the maximally intended dose is reached, up to 10 additional patients may be enrolled at this dose level to confirm the assessment and to collect additional safety, PK and PD data to aid in determining the recommended dose of APR-246 in combination with venetoclax and rituximab.

Table 3. APR-246 Dose Levels

Dose Modification	APR-246 Dose
Dose Level 1	APR-246 1.5 g/day 0.5 g (for first 45 minutes) + 1.0 g (for 5 hours 15 minutes)
Dose Level 2	APR-246 3.0 g/day 1.0 g (for first 45 minutes) + 2.0 g (for 5 hours 15 minutes)
Dose Level 3	APR-246 4.0 g/day 1.33 g (for the first 45 minutes) + 2.66 g (for 5 hours 15 minutes)

Prior to initiation of study treatment with APR-246 administered IV in combination with venetoclax and rituximab (during treatment cycles 2-7), patients will receive APR-246 alone on Day 1 and Day 2 of the 7-day monotherapy lead-in period, during which PK and PD of APR-246 following IV and PO administration will be evaluated. On Day 1 of the monotherapy lead-in period, APR-246 will be administered IV at the assigned cohort dose. On Day 2, APR-246 will be administered PO at the dose of 500 mg. This dose may be increased based on emerging PK data to determine dose linearity after oral dosing. Patients will be required to fast for at least 10 hours prior to APR-246 PO administration. Furthermore, a sub-group of patients may receive an oral dose of APR-246 in combination with a standard high-fat meal to determine the effect of food on APR-246 absorption.

Additional dose levels may be explored if warranted based on emerging DLT, safety, PK, and/or PD data. In addition, patients who have received at least 3 cycles of therapy at the assigned dose cohort level may advance to the next higher dose level once the next higher dose level has been declared safe by the DRT.

Responses will be assessed according to response criteria for RT ([Appendix V](#)) via blood, BM, and imaging (positron emission tomography [PET]/computed tomography [CT]). Response assessments are to be performed every 3 cycles and PET-CT scanning is recommended. For patients who achieve CR, imaging may be omitted, and minimal residual disease (MRD) assessment will be completed using flow cytometry and/or molecular techniques from the BM and/or peripheral blood.

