5.1.4 Dose-Limiting Toxicity

All TEAEs are relevant to the determination of DLTs unless they are clearly and solely due to the disease under study. The DLT evaluation period will be up to 91 days (7 days of APR-246 monotherapy plus 84 days for Cycle 1-3 with combination therapy) after the first dose of APR-246 is administered. A DLT is defined as any of the following TEAEs using the National Cancer Institute Common Terminology Criteria for Adverse Events (NCI-CTCAE), as follows:

- Any neurologic toxicity of grade 4
- Any grade ≥ 3 non-hematologic toxicity except for:
 - First occurrence of grade 3 electrolyte abnormalities and/or creatinine CL decrease resolving to grade 2 (or baseline if baseline is grade ≥ 2) within 48 hours with supportive treatment.
 - Grade 3 fatigue, nausea, vomiting, diarrhea or other manageable constitutional symptom(s) that is/are responsive to supportive therapy.
 - Grade 3 infection responding to appropriate antimicrobial therapy.
 - Any neurologic toxicity of grade 3 that does not return to grade ≤ 1 or baseline within 7 days.
- Any grade ≥ 3 hematologic toxicity will be considered a DLT except for:
 - Grade 3 neutropenia without fever
 - Grade 4 neutropenia without fever lasting 8 days or less
 - Grade 3 thrombocytopenia that does not result in bleeding or transfusion
 - Grade 3/4 lymphopenia/lymphocytosis
 - Grade 3/4 WBC decreased
 - Grade 3/4 WBC increased

Any toxicity, regardless of the NCI-CTCAE v5.0 grade, resulting in discontinuation, dose reduction or treatment with less than 75% of planned doses of APR-246 study drug, will be reviewed by the DRT, and will be considered a DLT unless clearly and solely related to the disease under study. The DRT will consist of the Medical Monitor, Site Principal Investigators, and other clinical research personnel that the Sponsor may deem appropriate.

G-CSF support for the management of neutropenia and prophylactic antimicrobial therapy are allowed, including during the DLT period.

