³ For patients with Gilbert's syndrome, these dose modifications apply to changes in direct bilirubin only.

⁴ LFTs include albumin, ALT, AST, total bilirubin (fractionated if total bilirubin >2.0×ULN), alkaline phosphatase.

Other Non-Hematological Toxicities

Toxicity	Worst toxicity ¹	Dose Modifications for APR-246
Infusion-Related Reaction	Grade 1	Maintain dose level.
	Grade 2	Maintain dose level; Symptomatic management (e.g., antihistamines, corticosteroids, narcotics, IV fluids)
	Grade 3	If resolved (to grade ≤1) in <4 hours with treatment interruption and medical therapy (e.g., antihistamines, corticosteroids, narcotics, IV fluids), continue same dose level and rate. If not resolved in < 4 hours despite treatment interruption and maximal medical therapy, stop infusion and ↓ 1 dose level for subsequent dose
	Grade 4	Permanently discontinue patient from APR-246.
	Grade 1	Maintain dose level. Monitor subject and provide supportive care measures as clinically indicated.
Nausea, Vomiting, and/or Diarrhea	Grade 2	Interrupt APR-246 dosing and monitor subject; treat promptly. Resume at current dose level if toxicity resolves to grade ≤1 or baseline, with or without use of supportive care measures, within 72 hours of onset. If toxicity does not resolve to grade ≤1 within 72 hours despite maximal medical intervention(s), then reduce APR-246 by 1 dose level once the

Toxicity	Worst toxicity ¹	Dose Modifications for APR-246
		toxicity resolves to grade ≤ 1 or baseline. If unable to reduce APR-246 dose, discuss with study Medical Monitor before resuming or discontinuing treatment. For subsequent doses of APR-246, pre-medication with prophylactic supportive therapy should be given if clinically indicated.

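### Table 11 gives two incompatible instructions for a grade 4 CNS event: resume or reduce APR-246 (Grade ≥3 row), or stop it for good (Grade 4 row)

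*Combined protocol and SAP*

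**What the plan says.** Table 11 in Section 5.3.2.5 sets the APR-246 action by worst grade of CNS toxicity. Its four rows are Grade 1, Grade 2, Grade ≥3 and Grade 4.

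- **Grade ≥3 row, event settles.** The infusion is stopped and the event treated. If it falls to grade ≤1 in no more than 2 "hours from onset, infusion may resume at the Investigator"'s discretion.
- **Grade ≥3 row, event does not settle.** After interruption and "maximal medical therapy, infusion should be discontinued for that day". The subsequent dose is one level lower. If no reduction is possible, the case goes to the Medical Monitor.
- **Grade 4 row.** "Permanently discontinue patient from APR-246", with no condition attached.

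The paragraph above the table covers any clinical AE of grade ≥3. If it resolves to grade ≤1 within 2 hours, "the infusion may be resumed at the same infusion rate". Grade 4 is not excepted.

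**The concern.** The two last rows overlap at grade 4, and they lead to different treatment. One leaves the patient on APR-246, either the same day or at a reduced dose later. The other ends APR-246. No precedence rule appears in Section 5.3.2.5 or elsewhere in the protocol.

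The decision is made during a 6-hour infusion and inside a 2-hour window, so the site will act on what the table and paragraph say. The matter at stake is the safety and later exposure of the individual patient. Neurologic toxicity has its own DLT criteria (Section 5.1.4), stopping criterion (Section 8.4) and exclusion criterion (Section 4.8). The neurologic stopping criterion applies only if the event has not returned to grade ≤1 or baseline within 7 days. On its own it would not catch a grade 4 event that settles within 2 hours and is then re-challenged.

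**Working it through.** The plan states no figure on this point, so there is none to reproduce. The check has three parts.

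**1. Rows matched by each grade**

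| CNS event grade | Table 11 rows that apply | Count |
|---|---|---|
| 1 | Grade 1 | 1 |
| 2 | Grade 2 | 1 |
| 3 | Grade ≥3 | 1 |
| 4 | Grade ≥3 and Grade 4 | 2 |

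The overlap is not confined to one table cell, because the paragraph above the table uses grade ≥3 as well. The infusion-related reaction rows of Table 10 (Section 5.3.2.4) show the clean form. There Grade 3 stands alone ("continue same dose level and rate" if resolved in under 4 hours, otherwise one level down), and Grade 4 is permanent discontinuation.

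**2. Dose at stake**

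Inputs: Table 3 gives a loading dose over 45 minutes (0.75 h) and a maintenance dose over 5 h 15 min (5.25 h). Dose Level 3, for example, is "1.33 g (for the first 45 minutes) + 2.66 g (for 5 hours 15 minutes". APR-246 is given "once weekly, on Days 1, 8 and 15 of each cycle", that is, three doses per cycle.

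*Event settles in ≤2 hours and the infusion resumes.* Assuming a constant maintenance rate, the undelivered remainder at time t hours (t ≥ 0.75) is M − (M / 5.25) × (t − 0.75), where M is the maintenance dose. At t = 3 this is M × (1 − 2.25 / 5.25) = M × 0.571.

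| Level | M, remainder at 0.75 h | Remainder at 3 h |
|---|---|---|
| 1.5 g | 1.0 g | 1.0 × 0.571 = 0.57 g |
| 3.0 g | 2.0 g | 2.0 × 0.571 = 1.14 g |
| 4.0 g | 2.66 g | 2.66 × 0.571 = 1.52 g |

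The remainder at 0.75 h is about two-thirds of the dose. Three hours is only an illustrative time.

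*Event does not settle.* The Grade ≥3 row allows later doses one level down:

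- from 4.0 g: 3 × 3.0 g = 9.0 g per cycle;
- from 3.0 g: 3 × 1.5 g = 4.5 g per cycle;
- from 1.5 g: Table 3 has no lower level, so the row refers the case to the Medical Monitor.

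Under the Grade 4 row the figure is 0 g in each case.

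**3. Effect on the DLT count**

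Section 5.1.4 lists "Any neurologic toxicity of grade 4" as a DLT. Within the evaluation period the event therefore counts whichever row the site follows, unless it is clearly and solely due to the disease. The overlap does not move the escalation decision.

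**The case against.** The best answer is that the table resolves itself. It has a dedicated, unconditional Grade 4 row, which would have no function if the Grade ≥3 row governed grade 4. Table 10 also ends APR-246 permanently at grade 4 for creatinine, bilirubin, AST/ALT and infusion-related reactions. This is very likely the intent. It does not settle the printed text, because the protocol does not treat grade 4 uniformly. In Table 10, grade 4 nausea, vomiting or diarrhea goes to the Medical Monitor, and any other grade 3 or 4 toxicity is delayed and then reduced one level. Continued dosing after a grade 4 event is thus an accepted option elsewhere, and a literal reading of the Grade ≥3 row is plausible.

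A second point is that resumption is only permitted, so an investigator who declines to resume satisfies both rows. That is true where the event settles. But an investigator who does resume is also following the text, and in doing so breaches the Grade 4 row. Where the event does not settle, the two rows contradict each other outright.

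Third, there are general safeguards: holding treatment under Table 6, clinical judgment and Medical Monitor advice, discontinuation for unacceptable risk (Section 4.10.1), and the 7-day neurologic stopping criterion (Section 8.4). They make unreviewed re-dosing less likely, but none says which row governs.

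Two criticisms stand. The gram figures describe what is at stake in a single case and do not estimate how often it would arise. And grade 4 nausea judged to be of CNS origin, like the general guidance in Table 6, can still point to a different action from Table 11. Those overlaps already exist with the current Grade 4 row; relabelling neither creates nor removes them.

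**Conclusion.** The concern holds: Section 5.3.2.5 is wrong as written. A grade 4 CNS event is subject both to a rule that allows APR-246 to continue and to one that ends it, with no stated precedence. For one patient, the difference is up to 1.0, 2.0 or 2.66 g on the day, or 9.0 g or 4.5 g per later cycle against none. The same-day figures assume an event after the loading phase; the hour-3 figures also assume a constant maintenance rate. The later figures assume all three weekly doses are given at the reduced level.

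The scope is narrow. Only grade 4 CNS events are affected, and the readable text gives no rate for them. The consequence is for patient safety and exposure, with no change to DLT counting. It should be corrected, since it is an operative dosing instruction for a toxicity the protocol singles out.

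**What to change.** In Table 11, relabel the Grade ≥3 row as Grade 3. In the paragraph above it, change grade ≥3 to grade 3 and add a sentence: *A grade 4 CNS event requires permanent discontinuation of APR-246.* Each grade then maps to one row, the paragraph agrees with the table, and the structure matches the infusion-related reaction rows of Table 10.

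The cost is one row label, one symbol and one sentence in Section 5.3.2.5. Design, sample size and data collection are unchanged.

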5.3.2.6 Management of Nausea, Vomiting, and Diarrhea

Prior to starting study treatment, patients should be evaluated to determine risk for nausea, vomiting, and/or diarrhea based on medical history and concomitant medications. Anti-nausea, anti-emetic, and/or anti-diarrheal medications should be initiated in patients with intermediate or high risk for nausea, vomiting, or diarrhea. Patients who experience nausea, vomiting, and/or diarrhea in association with APR-246 administration should be prescribed appropriate rescue treatment and prophylaxis (e.g., anti-nausea, anti-emetics, or anti-diarrheal medication).

A list of suggested rescue medications for nausea and vomiting is provided below in [Table 12](#).

Table 12. Medications for Management of Nausea and Vomiting

Drug	Dosage	QT Interval Prolongation ^a
Ondansetron	8 mg PO administered 30 minutes before the start of infusion or per label	Yes
Dolasetron	100 mg PO administered within one hour before start of infusion or per label	Yes
Palonosetron	0.5 mg PO administered approximately one hour prior to the start of infusion or per label	No
Prochlorperazine	10 mg PO three times daily. Continue until the end of Day 4 of the cycle. When used prophylactically in subsequent cycles, start the day prior to Day 1 administration of APR-246	No

^a Please refer to Section [5.3.2.3](#) for details on concurrent administration of medications known to cause QTc interval prolongation.

Monitor electrolyte levels and renal function during the course of study treatment and institute appropriate supportive care measures, such as electrolyte and/or fluid repletion, in the setting of vomiting and/or diarrhea.

5.3.2.7 Management of Infusion Reactions Associated with APR-246 Administration

If a patient experiences an infusion reaction during the study, the infusion may be stopped and appropriate medical care (e.g., epinephrine, oxygen, H1 and H2 antagonists, and/or corticosteroids) administered⁵⁴. Consultation with the Medical Monitor before additional administration of APR-246 is encouraged.

If the patient develops an acute infusion reaction (grade ≥ 2), the infusion should be interrupted until the reaction has resolved to grade ≤ 1 . Premedication (e.g., systemic corticosteroids) may be used as required.

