5.2 Dose Interruptions/Withholding

Study treatment, including APR-246, venetoclax, and/or rituximab, may be withheld from a patient based on the Investigator's decision in the event of intercurrent illness, AE, administrative reasons, or other reasons. If the patient's condition subsequently improves, or the situation that resulted in withholding study drug rectifies itself, the Investigator may resume dosing as soon as possible, unless the delay is more than 4 weeks. For study treatments held longer than 4 weeks, the Investigator should consult with the Medical Monitor before study treatments are resumed.

Dose management guidelines in [Table 5](#) should be followed for each occurrence of a grade ≥ 3 hematologic toxicity or those in [Table 6](#) for non-hematologic toxicity.

Table 5. Dose management guidelines for new onset hematologic toxicities

Toxicity	Occurrence	APR-246	Venetoclax	Rituximab
Grade 3 hematologic toxicity with fever and/or infection; or grade 4 hematologic toxicity	1 st occurrence • Hold all study treatments until blood count(s) return to baseline or grade ≤1 and fever and/or infection resolve if present. Treat promptly.	
 Consider reducing APR-246 by one dose level from starting dose for all future cycles of treatment if toxicity does not resolve to grade ≤1 within 7 days from onset date despite maximal medical intervention(s). If unable to reduce APR-246 dose, discuss with study Medical Monitor before resuming or discontinuing treatment. Initiate or reassess prophylaxis measures. Refer to Section 5.3.2.2 for supportive management guidelines specific to infection prophylaxis and neutropenia. 	
 Refer to Section 5.3.3.1 for venetoclax dose modification guidelines. 	
 Resume rituximab at same dose level once event resolves to baseline or grade ≤1, except in case of serious infection. For patients diagnosed with a serious grade ≥3 infection, rituximab should be permanently discontinued.

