Occurrence	APR-246	Venetoclax	Rituximab
1 st occurrence • Hold all study treatments until toxicity returns to baseline or grade ≤1. Treat promptly.	
Consider reducing APR-246 by one dose level from current dose for all future cycles of treatment if toxicity does not resolve to grade ≤1 within 7 days from onset date despite maximal medical intervention(s).If unable to reduce APR-246 dose, discuss with study Medical Monitor before resuming or discontinuing treatment.	Refer to Section 5.3.3.1 for venetoclax dose modification guidelines.	Resume rituximab at same dose level once event resolves to baseline or grade ≤1, except in case of serious infection. For patients diagnosed with a serious grade ≥3 infection, rituximab should be permanently discontinued.
2 nd occurrence • Hold all study treatments until toxicity returns to baseline or grade ≤1	
Consider reducing APR-246 by one dose level from starting dose for all future cycles of treatment.	Refer to Section 5.3.3.1 for venetoclax dose modification guidelines.	Reduce rituximab dose from 500 mg/m ² to 375 mg/m ² . If unable to reduce rituximab, discuss with study Medical Monitor before resuming or discontinuing rituximab. For patients diagnosed with serious grade ≥3 infection, rituximab should be permanently discontinued.
3 rd occurrence • Hold all study treatments until toxicity returns to baseline or grade ≤1. Treat promptly.	
Consult with study medical monitor to determine if further dose modifications of study treatment(s) are medically necessary or if study treatment(s) should be discontinued.		

Actions noted in table above for rituximab are specific to toxicities occurring during Cycles 2 through 7. Rituximab may be reduced by one dose level, from 500 mg/m² to 375 mg/m², when clinically indicated. Please consult with study Medical Monitor to discuss dose modification(s) for rituximab.

Treatment may be discontinued if a TEAE has not improved (to an acceptable grade) or resolved after ≥ 4 weeks, at the discretion of the Investigator. Please consult study Medical Monitor if this situation occurs.

Patients experiencing 3 occurrences of the same toxicity should be discussed with the study Medical Monitor before study treatments are resumed.

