^a During APR-246 monotherapy lead-in, ECG should be collected in triplicate within 30 minutes prior to the infusion of APR-246 and within ±30 min of end of the 6-hour infusion (EOI) of APR-246 on Days 1 – 2. QTcF must be calculated from a mean of all three ECG readings.

If a patient starts treatment with a medication associated with QT interval prolongation, such as triazole antifungals, fluoroquinolones, and anti-emetics, while receiving study treatment, an additional pre- and post-dose (within 30 minutes prior to the infusion of APR-246 and within ±30 min of 6 hours after start of infusion) ECG should be performed on the next APR-246 treatment day.

5.3.2.4 Management Guidelines for APR-246 Dose Modifications and Criteria for Treatment Interruption and Re-Initiation with Treatment-Related Adverse Events

Table 10. Recommendations for APR-246 Dose Modifications and Criteria for Treatment Interruption and Re-Initiation with Treatment-Related Adverse Events

Renal Toxicities

Parameter	Worst toxicity ¹	Dose Modifications for APR-246
Serum Creatinine	Grade 1 (<1.5 × baseline)	Maintain dose level
	Grade 2 (>1.5-3.0 × baseline)	Omit dose until resolved to grade ≤1, then: If first occurrence, then maintain dose level If second or more consecutive occurrence, then ↓ 1 dose level
	Grade 3 (>3.0-6.0 × baseline)	Omit dose until resolved to grade ≤1, then: ↓ 1 dose level If not resolved or resolved in >7 days, evaluate if other contributing factors are present. If none, or after consideration of best interest of the patient, discontinue patient from APR-246. If other factors present, consider continuing after ↓ 1 dose level
	Grade 4 (>6.0 × baseline)	Permanently discontinue patient from APR-246

¹ Common Terminology Criteria for Adverse Events (CTCAE) version 5.

Hepatic Toxicities ¹

Parameter	Worst toxicity ²	Dose Modifications for APR-246
Bilirubin ³	Grade 1 (>ULN-1.5×ULN)	Maintain dose level with LFTs ⁴ monitored as per protocol
	Grade 2 (>1.5-3.0×ULN) with ALT or AST ≤3.0×ULN	Omit dose until resolved to grade ≤1, then: If resolved in ≤7 days, if first occurrence, then maintain dose level If second or more consecutive occurrence or if resolved in >7 days, then ↓ 1 dose level

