	Grade 3	
1st occurrence: Interrupt APR-246 dosing and monitor subject; treat promptly.
 
Resume at current dose level if toxicity resolves to grade ≤ 1 or baseline, with supportive care measures, within 72 hours of onset.
 
If toxicity does not resolve to grade ≤ 1 within 72 hours despite maximal medical intervention(s), then reduce APR-246 by 1 dose level once the toxicity resolves to grade ≤ 1 or baseline.
 
If unable to reduce APR-246 dose, discuss with study Medical Monitor before resuming or discontinuing APR-246.
 
For subsequent doses of APR-246, pre-medication with prophylactic supportive therapy should be given.
 
2nd occurrence: Interrupt APR-246 dosing and monitor subject; treat promptly.
 
Reduce APR-246 by 1 dose level if the toxicity resolves to grade ≤ 1 or baseline within 72 hours of onset.
 
If toxicity does not resolve to grade ≤ 1 despite maximal medical intervention(s) within 72 hours of onset, then consult with study Medical Monitor before resuming or discontinuing APR-246.
 
If unable to reduce APR-246 dose, discuss with study Medical Monitor before resuming or discontinuing treatment.
 
Prior to subsequent doses of APR-246, reassess prophylactic supportive therapy regimen and adjust as clinically indicated.
 
3rd occurrence: Interrupt APR-246 dosing and monitor subject; treat promptly. Consult with study Medical Monitor before resuming or discontinuing APR-246.

	Grade 4	Interrupt APR-246 dosing and monitor subject; treat promptly. Consult with study Medical Monitor to discuss dose modification or permanent discontinuation of APR-246.
Any Other Toxicity	Grade 3 or 4	
Delay dose until resolution to grade ≤ 1 or baseline, then $\downarrow 1$ dose level.
 
If unable to reduce APR-246 dose, discuss with study Medical Monitor before resuming or discontinuing APR-246.

¹ Common Terminology Criteria for Adverse Events (CTCAE) version 5.

Treating physicians should use clinical judgment and may consult the Medical Monitor for additional guidance with APR-246 dose modifications.

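### Section 5.3.2.7 and Table 6 leave re-dosing open after a grade 4 APR-246 infusion reaction; Table 10 bars it, and no visible text says Table 10 governs

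*Combined protocol and SAP*

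**What the plan says.** Three visible texts bear on a severe infusion reaction to APR-246.

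- **Section 5.3.2.7.** The first paragraph lets the infusion be stopped and supportive care given, and adds: "Consultation with the Medical Monitor before additional administration of APR-246 is encouraged". The second covers acute reactions of grade 2 or higher, for which "the infusion should be interrupted until the reaction has resolved" to grade 1 or lower. Premedication is allowed as needed. Grade 4 is not treated separately.
- **Section 5.2 and Table 6.** Section 5.2 says its dose-management guidelines "should be followed for each occurrence of a grade" 3 or higher hematologic toxicity (Table 5) and, in the same sentence, sends non-hematologic toxicity to Table 6. Table 6 covers grades 3 and 4 together. Its first-occurrence instruction is: "Hold all study treatments until toxicity returns to baseline or grade ≤1. Treat promptly". For APR-246 it then says to consider a one-level reduction in later cycles if the event has not resolved to grade 1 or lower within 7 days.
- **Section 5.3.2.4, Table 10, Infusion-Related Reaction rows.** Grade 2 keeps the dose level with symptomatic treatment. Grade 3 continues at the same dose and rate if resolved in under 4 hours. "If not resolved in < 4 hours despite treatment interruption and maximal medical therapy", the infusion is stopped and the next dose drops one level. Grade 4 reads: "Permanently discontinue patient from APR-246".

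Table 10 is captioned "Recommendations for APR-246 Dose Modifications and Criteria for Treatment Interruption and Re-Initiation with Treatment-Related Adverse Events" and is followed by this sentence: "Treating physicians should use clinical judgment and may consult the Medical Monitor for additional guidance with APR-246 dose modifications".

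**The concern.** A grade 4 infusion reaction is life-threatening, and the question that follows is whether the patient may ever receive the drug again. Table 10 says no. Interrupting until recovery, as 5.3.2.7 directs, implies that the drug may be restarted, and Table 6 speaks of the dose in future cycles. A clinician managing a reaction would naturally open the section named for infusion reactions, and that section does not lead to the grade 4 row.

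What is at stake is re-exposure of an individual patient, and different handling of the same event across as many as 10 sites. The dose-escalation arithmetic is not affected.

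**Working it through.** No figure in the plan depends on this point, so the check is a comparison of texts.

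**Step 1. Action by grade.**

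| Reaction | 5.3.2.7 | Table 6 (first occurrence) | Table 10 |
|---|---|---|---|
| Grade 2 | Interrupt until grade 1 or lower | Not covered | Keep dose level, treat symptoms |
| Grade 3, unresolved | Interrupt until grade 1 or lower; no time limit | Hold until recovery; consider one-level reduction if unresolved within 7 days | If not resolved in under 4 hours, stop and reduce one level |
| Grade 4 | Same as grade 2 | Same as grade 3 | Permanent discontinuation |

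At grade 2 the texts are compatible: one concerns the running infusion, the other the dose level. At grade 3 they differ in timing (4 hours against 7 days) and in force (a set reduction against one to be considered). At grade 4 they differ in outcome: one of three ends APR-246, and two interrupt or hold it until recovery.

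**Step 2. Is there a precedence rule?** Table 10 is named twice in the visible text: in the list of tables and in its own caption. That leaves 0 cross-references from section 5.2 or section 5.3.2.7. The introduction to section 5.3.2 lists QTc prolongation, CNS events, nausea and vomiting, and infections; it neither mentions infusion reactions nor ranks the texts. The Table 10 caption states what the table covers, not that it overrides anything, and the sentence after it defers to clinical judgment.

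**Step 3. Does the protocol link its rules elsewhere?** Yes. Section 5.3.2.5 also interrupts an infusion and allows it to resume, but it cites Table 11, which has a grade 4 permanent-discontinuation row. Table 5 points to 5.3.2.2. The venetoclax column of Table 6 points to 5.3.3.1, while its APR-246 column points nowhere.

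**Step 4. Do other rules close the gap?**

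- Section 4.10.1 requires discontinuation when the Investigator judges continued participation an unacceptable risk. This rests on individual judgment.
- Section 7.1.2.6 requires SAE notification within 24 hours of awareness, and 7.1.2.7 provides Medical Monitor review. Neither requires a hold before the next dose.
- Section 5.2 calls for Medical Monitor consultation when treatment has been held longer than 4 weeks. A reaction that clears in hours would not trigger it.
- Under 5.1.4 a grade 4 reaction in the DLT window counts as a DLT unless clearly and solely due to the disease. This acts on the cohort, and the window ends with Cycle 3, whereas APR-246 may run for up to 24 cycles.
- Section 8.4 suspends enrollment when more than 1 patient has a medically equivalent SAE not attributable solely to the disease. This acts on enrollment.

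These limit the harm, but none states the fixed grade 4 rule in Table 10.

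**The case against.** The strongest reply is that this is a missing cross-reference and not a contradiction. Section 5.3.2.7 governs the infusion in progress and never says that APR-246 may be resumed after grade 4. A site that interrupts, treats and then permanently discontinues complies with both texts. Table 10's caption covers re-initiation, it has a row for this exact event and grade, and a specific row ordinarily controls a general one. Table 6 never names infusion reactions, and its first-occurrence APR-246 cell has no explicit instruction to resume. Section 5.1.1 is blacked out and could hold the rule, since the rituximab counterpart, 5.1.3, does contain infusion-reaction instructions. If Table 10 is only advisory, the conflict softens.

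Much of this stands. The harmonized reading is available, and a careful site would probably choose the stricter row. The redaction means a governing rule cannot be excluded. But 5.3.2.7 is not purely acute care: it addresses further administration, makes consultation before it optional, and allows premedication. Table 6 is written for dosing in later cycles. Table 10's advisory title makes matters less settled, because an unconditional stop then sits in a table that does not claim to bind. Leaving the reader to infer precedence is a weak safeguard after a life-threatening reaction.

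**Conclusion.** The concern holds on the visible text. For a grade 4 APR-246 infusion reaction, Table 10 alone requires permanent discontinuation; 5.3.2.7 and Table 6 pause treatment until recovery, and nothing visible says which prevails. There is a smaller mismatch at grade 3.

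The size is a count of instructions, one against two, and not a risk: no infusion-reaction rate is visible, so the number of patients exposed to the ambiguity cannot be given. The conclusion assumes that the redacted section 5.1.1 contains no governing rule or pointer. Given the backstops, this should be corrected as a patient-safety ambiguity; it does not undermine the design.

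**What to change.** In 5.3.2.7, keep interruption for grade 2 or higher and add two statements:

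1. Resumption applies only to grades 2 and 3 and is subject to Table 10, including stopping the infusion and reducing one dose level when a grade 3 reaction has not resolved in under 4 hours.
2. Grade 4 means permanent discontinuation of APR-246, per Table 10.

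In 5.2, add one line saying that the event-specific rows of Table 10 take precedence over Table 6 for APR-246.

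The cost is protocol wording only. The change restates the sponsor's own stricter rule and adds no procedure, data collection or patients.
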